#### **4.3.2. Discontinuation from Treatment with Lapatinib and Capecitabine**

Subjects may withdraw from the study at any time.

Study treatment may be permanently discontinued for any of the following reasons:

- liver chemistry meeting the stopping criteria described in Section 5.13.1
- deviation(s) from the protocol
- disease progression
- request of the subject or proxy
- investigator's discretion
- subject is lost to follow-up
- study is closed or terminated.

The primary reason study treatment was permanently discontinued must be documented in the subject's medical records and the study eCRF. If the subject voluntarily discontinues treatment due to toxicity, 'AE' will be recorded as the primary reason for permanent discontinuation in the eCRF.

Subjects who require permanent discontinuation of either lapatinib or capecitabine must permanently discontinue both treatments in that combination and the reason for discontinuation must be recorded. Once a subject has permanently discontinued treatment with lapatinib and capecitabine, the subject will not be allowed to be re-treated and must be withdrawn from the study.

All subjects who discontinue treatment with lapatinib and capecitabine will have safety assessments at the time of discontinuation as specified in the Time and Events Schedule (Table 16 and Table 17) and in Section 7.1.8.

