#### **4.3.3. Subject Completion**

A subject will be considered to have completed the study if the subject completes 24 weeks of treatment with lapatinib and capecitabine, or if cancer progresses or the subject dies during treatment, whichever is sooner. The cause of death must be recorded in the eCRF. A subject will be considered to have withdrawn from the study prematurely if

treatment is permanently stopped due to toxicity, or the subject has withdrawn consent, or the subject is no longer being followed at the investigator's discretion.

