**Time to onset of the first episode of diarrhoea**

The time to onset of the first episode of diarrhoea of any grade of severity will be summarised by treatment arm using Kaplan-Meier methods. Subjects who complete the study or withdraw prematurely without experiencing an episode of diarrhoea will be censored at the date of withdrawal or study completion. The Kaplan-Meier estimate of the proportion of patients experiencing an episode of diarrhoea will be presented for each 3-week time interval by treatment group. Estimates and 95% confidence intervals for the 25th percentile, median and 75th percentile will be provided by treatment group. Treatment groups will be compared using the log-rank test, or the Wilcoxon test in the case of non-proportional hazards.

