Study completion will be at the end of 24 weeks treatment with lapatinib and capecitabine, or disease progression, unacceptable toxicity or subject withdrawal if this is sooner. SAEs and other safety data will be reported beyond 24 weeks in subjects who continue treatment with lapatinib and capecitabine until disease progression in countries where the Sponsor is supplying lapatinib and capecitabine. SAEs will be followed up until resolution or stabilization of the event or until the subject is lost to follow-up.

The efficacy of prophylactic octreotide in reducing the frequency and severity of diarrhoea is the primary endpoint of this study. Each episode of diarrhoea will be recorded by the investigator as an AE in the eCRF in accordance with the standard AE reporting procedure. Actions associated with the management of diarrhoea (use of anti-diarrhoeal medication, unscheduled visits to healthcare professionals, treatment interruption, rehydration) will be recorded in the eCRF.

Subjects will complete the DMD and the FACIT-D to provide an additional perspective on the effects of treatment-associated diarrhoea.

Diarrhoea, nausea and vomiting, dermatological events, hepatobiliary, cardiovascular and respiratory events have been identified as events of special interest relating to lapatinib. Hand and foot syndrome has been identified as an event of special interest relating to capecitabine. There are no events of special interest relating to octreotide.

The schedule of all assessments is presented in [Table 1-1](#) for subjects who receive octreotide and [Table 1-2](#) for subjects who do not receive octreotide.

Table 1-1 Time and events schedule; Subjects who receive octreotide.

	Screen ¹	Octreotide Dose 1	Lapatinib and Capecitabine Cycle ^{9,10}			Withdrawal from Study Treatment or End of Study ¹⁴
			Cycle 1	Cycle 2 (Octreotide Dose 2)	Cycles 3 to 8	
Procedures						
Informed Consent	X					
Inclusion/Exclusion Criteria	x ²	x ²				
Demographics	X					
Breast Cancer Medical/Surgical and Treatment History	X					
Efficacy and Safety Assessments						

AE/Toxicity Assessment		x	x	x	x	x ¹⁵
Disease Assessment	x ³	(x) ⁵	(x) ⁵	(x) ⁵	(x) ⁵	x
PROs ⁶		x ⁷	x ¹¹	x	x	x
Concurrent Medications	X	x	x	x	x	x
Physical Exam	X					x
Weight, Height, Vital Signs (Temp, BP, pulse)	X					x
ECOG Performance Status	x ⁴					x
Cardiac function	X					x ¹⁶
ECG	X					(x) ¹⁷
Lab Assessments						
Liver function	X	(x) ⁵	(x) ⁵	(x) ⁵	(x) ⁵	x
Pregnancy Test	X					x
Study Treatments						

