2.6.1.3 Time to onset of the first episode of diarrhoea

The time to onset (in days) of the first episode of diarrhoea of any grade of severity will be derived as ((date of first episode of diarrhoea – date of first dose of lapatinib and capecitabine) + 1) and it will be summarised by treatment group using Kaplan-Meier methods. Subjects who complete the study or withdraw prematurely without experiencing an episode of diarrhoea will be censored at the date of withdrawal or study completion.

The Kaplan-Meier estimate of the proportion of subjects experiencing an episode of diarrhoea will be presented for each 3 week cycle of lapatinib and capecitabine by treatment group. Estimates and 95% confidence intervals for the 25th percentile, median and 75th percentile will be provided by treatment group.

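### SAP 2.6.1.3 censors progression, death and treatment discontinuation, then labels the Kaplan-Meier result a proportion of subjects; it overstates that proportion, mainly in later cycles

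*SAP*

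**What the plan says.** SAP 2.6.1.3 measures time from the first lapatinib/capecitabine dose to the first episode of any grade. Its censoring rule is: "Subjects who complete the study or withdraw prematurely without experiencing an episode of diarrhoea will be censored at the date of withdrawal or study completion". It describes the output so: "The Kaplan-Meier estimate of the proportion of subjects experiencing an episode of diarrhoea will be presented for each 3 week cycle". The 25th, 50th and 75th percentiles are also reported. The protocol section of the same name uses the same rule and label: "The Kaplan-Meier estimate of the proportion of patients experiencing an episode of diarrhoea will be presented for each 3-week time interval by treatment group".

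What counts as withdrawal or completion is set elsewhere:

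- SAP 1.1 ends the study at 24 weeks, "or disease progression, unacceptable toxicity or subject withdrawal if this is sooner".
- Protocol 4.3.3 counts a subject as a completer at 24 weeks, "or if cancer progresses or the subject dies during treatment, whichever is sooner".
- Protocol 4.3.2 says that after permanent discontinuation of lapatinib and capecitabine "the subject will not be allowed to be re-treated and must be withdrawn from the study".

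SAP 5.3.2 specifies only the product-limit estimator. Neither document names a competing event or states an independent-censoring assumption for this endpoint. SAP 2.6.1.2 separately gives the crude any-grade proportion over the whole treatment period. The protocol's log-rank or Wilcoxon comparison does not appear in SAP 2.6.1.3.

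**The concern.** After death no episode can occur. After progression or permanent discontinuation none can occur on this regimen, and follow-up stops. Kaplan-Meier treats these subjects as if they went on to have diarrhoea at the rate of those still on treatment. That is a legitimate estimate of a hypothetical on-treatment risk if censoring is independent. It is not the share of subjects who have an episode.

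The censored events are not rare. With a constant hazard and median 28.6 weeks, 1 - 0.5^(24/28.6) = 44% would progress or die within 24 weeks in the absence of diarrhoea; with 23.9 weeks, 50%. Because the output is descriptive, the displayed number is the whole result, so its label has to be true.

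**Working it through.** Neither document gives a figure for time to onset, so there is no planned value to reproduce. The size has to be modelled.

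**Inputs from the protocol**

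- Any-grade incidence: 45% (121/269, EGF111438), 65% and 69% (EGF100151).
- Onset, EGF111438 (Table 4): 67 of 121 on days 1-14, 22 on days 15-28, 32 later; mean 28.6 days.
- Time to progression or PFS: medians 23.9, 27.1 and 28.6 weeks.

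**Assumptions**

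- Onsets are uniform within the first two bins, then exponential with mean 53 days after day 28. The implied mean is (67×7 + 22×21 + 32×81)/121 = 29.1 days, close to 28.6.
- The 65% and 69% cases use the same shape, scaled up.
- Progression is exponential from day 1 and independent of diarrhoea, with no other withdrawal.
- Source-study incidence is read as cumulative incidence.

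**Formulas.** Let f(u) be the density of first episodes actually occurring, and G(u) = exp(-λu), with λ = ln 2 / median.

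- Cumulative incidence: F(t) = ∫ f(u) du
- Kaplan-Meier: 1-KM(t) = ∫ f(u)/G(u) du

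Since G ≤ 1, 1-KM can never be below F. Each onset is inflated by 1/G(u), so late onsets carry most of the excess.

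**Example: 45%, 23.9 weeks.** λ = 0.6931/167.3 = 0.004143 per day; exp(14λ) = 1.0597; exp(28λ) = 1.1230. The onset shares are 0.2492, 0.0818 and 0.1190.

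- Days 1-14: (0.2492/14)(0.0597/0.004143) = 0.257
- Days 15-28: (0.0818/14)(0.0633/0.004143) = 0.089
- Days 29-168, with k = 1/53 - λ = 0.01472: (0.1190/53)(1.1230)(1 - exp(-140k))/k = 0.149

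So 1-KM = 0.495. F = 0.2492 + 0.0818 + 0.1190(1 - exp(-140/53)) = 0.442. The excess is 5.4 points. Both quantities scale with incidence.

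**Week 24 (1-KM v cumulative incidence, %)**

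| Median | 45% | 65% | 69% |
|---|---|---|---|
| 28.6 wk | 48.5 v 44.2 (+4.4) | 70.1 v 63.8 (+6.3) | 74.4 v 67.7 (+6.7) |
| 27.1 wk | 48.8 v 44.2 (+4.7) | 70.5 v 63.8 (+6.7) | 74.8 v 67.7 (+7.1) |
| 23.9 wk | 49.5 v 44.2 (+5.4) | 71.5 v 63.8 (+7.8) | 75.9 v 67.7 (+8.2) |

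The same integrals stopped at day 21 give an excess of 0.9 to 1.6 points, and at day 63, 2.2 to 4.0 points.

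**Sensitivity at week 24**

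- Progression only after week 6 or 9, median kept: 1.1 to 3.4 points, and up to 4.8 with an assumed 10% other withdrawal. If the daily hazard is kept and merely starts later: 0.7 to 2.4.
- Progression from day 1 plus an assumed 10% other withdrawal: up to 9.7.
- No progression, only 5 to 15% withdrawal or death: 0.3 to 1.7.
- Late onsets uniform to day 168: 6 to 14. Constant diarrhoea hazard: 12 to 19.

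**Percentiles under the base model**

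- 25th: moves by a day or less.
- Median: about 2 days earlier at 69%. At 65%, F(28) = 0.65×89/121 = 0.478, so F reaches 50% at 28 - 53 ln(1 - 0.022/0.172) = about day 35, against day 28 to 29 for 1-KM. At 45% neither curve reaches 50%, although 1-KM gets to 50.5% at 23.9 weeks with 10% other withdrawal.
- 75th: at 69% and 23.9 weeks, 1-KM passes 75% around week 22, while cumulative incidence ends at 67.7%. At 27.1 or 28.6 weeks without other withdrawal, neither reaches it.

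**The case against.** The strongest reply is that little depends on this. The endpoint is secondary. The SAP tests nothing between arms on it. The trial stopped for futility with 62 enrolled, and the report is abbreviated. At an assumed 31 per arm, the base-case shift is about 0.45 to 0.93 of a standard error. SAP 2.6.1.2 already reports the crude proportion and lists every episode with its onset time. Kaplan-Meier with censoring at the end of treatment is also a recognised estimate of on-treatment risk, so relabelling alone would remove the false statement. All of this stands and limits the importance of the point. It does not make the label correct.

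Four stronger readings are tempting, and the documents do not support them.

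- **That the bias is 4 to 8 points as a fact.** It is one scenario. RECIST assessment is mandatory only at the end-of-study or withdrawal visit, so removal for progression at a constant rate from day 1 is a modelling choice.
- **That all reported percentiles are materially distorted.** Most onsets are early (median 12 days; 89 of 121 by day 28), so the lower percentiles move little.
- **That the report gives two figures for the same quantity.** The crude proportion counts onsets from randomisation (SAP 2.1.3.2 and 2.5.2.2), while the time-to-onset clock starts at the first lapatinib/capecitabine dose. In the octreotide arm these differ by the 7-day lead-in, so the two figures would differ anyway.
- **That the octreotide effect is biased.** The SAP makes no formal comparison here, and nothing in the documents shows that progression or withdrawal differs between arms.

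**Conclusion.** The point holds as one of estimand and labelling. Under the rule as written, the per-cycle figures are hypothetical on-treatment risks presented as proportions of subjects, and they are too high whenever a censored competing event precedes later onsets. That direction needs no assumed rate.

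The week 24 excess is about 4 to 8 points with progression from day 1, and about 1 to 5 points if it starts after 6 to 9 weeks. It can be well above 8 points if onsets are later than in EGF111438. These ranges rest on 45 to 69% incidence, the EGF111438 onset shape and independence of progression from diarrhoea; the 10% other withdrawal in the upper part of the lagged range is assumed.

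The excess is about 1 to 2 points at week 3 even in the base case. The main percentile risk is a 75th percentile printed although fewer than 75% of subjects ever have an episode, which needs high incidence with fast progression. The primary analysis is unaffected.

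**What to change.** In SAP 2.6.1.3 and 5.3.2, replace the Kaplan-Meier proportions by the Aalen-Johansen cumulative incidence per 3-week cycle with 95% CI. Treat death, progression and permanent discontinuation of lapatinib/capecitabine as competing events (PROC LIFETEST with EVENTCODE=). Censor only event-free 24-week completion and loss to follow-up, and take the percentiles from that curve.

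If the Kaplan-Meier curve is also kept, label it as on-treatment risk under independent censoring. Add a footnote that the crude proportion in 2.6.1.2 starts at randomisation and this curve at the first lapatinib/capecitabine dose.

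The cost is one changed procedure option, a derived event-type variable from disposition data already collected, and a few sentences. The downside is that upper percentiles may be reported as not reached, which would then be the accurate statement.

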2.6.1.4 Study treatment compliance

Inference of the efficacy of prophylactic octreotide will be made by summarising compliance to lapatinib and capecitabine separately by treatment group. Compliance will be derived as described in [Section 2.4.1](#).

A summary of compliance with prophylactic octreotide will be presented. Compliance will be derived as described in [Section 2.4.1](#).

2.6.1.5 Response

Response is a secondary aim of this study, as the sample size is relatively small and the study is not powered to detect a statistically significant difference in the response rate or the efficacy of lapatinib and capecitabine for octreotide vs. no octreotide subjects. However, overall response rate and clinical benefit response rate will be presented for interest. RECIST data to assess tumour size and new tumours will be collected as per clinical practice throughout the study. Data will be collected at baseline (screening) and end of 24 weeks of lapatinib and capecitabine treatment. Therefore overall response rate will be presented as response following 24 weeks of treatment, as subjects will not be followed up to progression or death. Therefore, the results of this analysis should be treated with caution and are for interest and exploratory purposes.

Overall response rate (ORR)

Overall response rate (ORR) is defined as the percentage of subjects achieving either a confirmed complete (CR) or partial (PR) tumour response at the end of the study (End of Study/Withdrawal visit). This will be based on the investigator's assessment of overall response.

Subjects with a not evaluable (NE) or missing response will be treated as non-responders; i.e. they will be included in the denominator when calculating the percentage.

The 95% CI for response rates in each group will be provided for the difference in response rates, as for the primary endpoint.

Clinical benefit response

Clinical benefit response (CBR) is defined as the percentage of subjects with a CR, PR or stable disease (SD) for at least 24 weeks. The CBR will be calculated using the investigator's assessment of response. Subjects who do not have measurable disease, or who have a missing or NE response will be treated as non-responders. The CBR in each treatment group and corresponding 95% confidence interval will be presented.

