## Study Assessments

The primary endpoint of LAP117314 is the proportion of subjects experiencing diarrhoea with a severity of Grade 2 and above, as defined by the NCI CTCAE, version 4.03. The frequency and severity of episodes of diarrhoea will be recorded at each visit, by completion of the AE modules in the eCRF. Action taken as a result of diarrhoea (anti-diarrhoeal medication, unscheduled visits to healthcare professionals, dose reduction or

delay in treatment with lapatinib and capecitabine, treatment withdrawal, and intravenous fluid rehydration) will be recorded in the eCRF at each visit.

All subjects will complete the baseline DMD and FACIT-D during the 3 days prior to randomisation, before any study-related treatment is administered. Subjects randomised to receive octreotide will complete a second baseline DMD and FACIT-D before starting the first cycle of treatment with lapatinib and capecitabine. Subjects will then complete the DMD every week and the FACIT-D every 3 weeks until the end of 24 weeks of treatment with lapatinib and capecitabine or subject withdrawal, whichever is sooner. The DMD and FACIT-D will not be completed beyond 24 weeks of treatment.

Disease status will be assessed prior to the start of treatment with lapatinib and capecitabine in accordance with the Response Evaluation Criteria In Solid Tumours (RECIST), version 1.1. Disease progression will be evaluated by the investigator in accordance with local clinical practice during the course of treatment with lapatinib and capecitabine, and in accordance with RECIST version 1.1 at the end of study visit (subject withdrawal or at the end of 24 weeks of treatment with lapatinib and capecitabine, whichever is sooner). Treatment with lapatinib and capecitabine may continue beyond 24 weeks until disease progression occurs, but there will be no further data collection of disease progression beyond 24 weeks of treatment.

The safety and tolerability of treatment with octreotide, lapatinib and capecitabine will be evaluated by AE and serious AE reporting at each visit until subject withdrawal or the end of 24 weeks of treatment with lapatinib and capecitabine. Serious AEs and other specific safety assessments will be reported in subjects who continue treatment with lapatinib and capecitabine beyond 24 weeks. Serious AEs will be followed up until resolution or stabilisation of the event or until the subject is lost to follow-up.

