### 7.1.11. Disease Assessments

Disease assessments and response evaluations will be determined according to the definitions established in RECIST version 1.1 [Eisenhauer, 2009]. The frequency and methodology of disease assessments will be in accordance with local clinical practice during treatment with lapatinib and capecitabine, but disease assessments in accordance with RECIST version 1.1 must be conducted at the early withdrawal or study completion visit.

Overall response will be determined at the end of study treatment or at early withdrawal. The possible combinations of tumour responses are described in Table 18 and in Table 19.

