## **Overall Response Rate**

Overall response rate (ORR) is defined as the percentage of subjects achieving either a confirmed complete (CR) or partial (PR) tumour response. The ORR will be calculated from the investigator's assessment of response. Subjects who do not have measurable disease or have an unknown or a missing response will be treated as non-responders when calculating the percentages and will contribute to the response rate-based analyses for the evaluation of CR, PR, stable disease (SD) and progressive disease. The ORR in each treatment arm and corresponding 95% confidence interval will be presented.

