2.1.3.2 Reference start date

There are three reference start dates:

- Age is an eligibility requirement and therefore the reference start date for age is the date of screening.
- The safety reference start date is the date of a subject receiving the first dose of study treatment (i.e., octreotide, lapatinib or capecitabine).
- The efficacy reference start date is the date of randomization and will be used to calculate study day for efficacy measures and baseline characteristics.

The reference start date for all other, non-safety assessments (i.e., tumor assessment, death, disease progression, tumor response, ECOG performance status, and patient reported outcomes (PRO)) is the date of randomization.

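### ORR requires a confirmed response that one mandated post-baseline RECIST assessment cannot supply, while the measurable-disease rule and the CBR start date are left inconsistent or unstated

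*SAP*

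**What the plan says.** **ORR.** Protocol 9.3.5.1.2 defines it as the "percentage of subjects achieving either a confirmed complete (CR) or partial (PR) tumour response". SAP 2.6.1.5 keeps the qualifier, adds the time point ("confirmed complete (CR) or partial (PR) tumour response at the end of the study") and relies on the investigator's assessment. Neither document gives a confirmation rule: no second scan, no interval.

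**Assessment schedule.** Protocol 7.1.11 states: "Overall response will be determined at the end of study treatment or at early withdrawal". Protocol sections 2 and 9.3.3.2 make RECIST 1.1 obligatory after baseline only at that end visit. Interim assessments follow local practice and are recorded in the eCRF when done (Protocol 7.1.6). Afterwards, according to the Protocol Summary, "there will be no further data collection of disease progression beyond 24 weeks of treatment".

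**Non-measurable disease.** For ORR the protocol says: "Subjects who do not have measurable disease or have an unknown or a missing response will be treated as non-responders". The SAP's ORR text names only not-evaluable and missing responses. Its CBR text names non-measurable disease as well.

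**CBR.** The SAP defines it as the "percentage of subjects with a CR, PR or stable disease (SD) for at least 24 weeks", without saying when the 24 weeks begin. SAP 2.1.3.2 has a general rule beginning "The reference start date for all other, non-safety assessments (i.e., tumor assessment, death, disease progression, tumor response", and sets that date to randomisation. The end visit is timed by 24 weeks of lapatinib plus capecitabine.

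**The concern.** ORR and CBR are the only tumour-control endpoints kept in the SAP's Table 1-3. They matter here because Protocol 3.2 accepts that delaying cancer therapy by 7 days in the octreotide arm may harm disease outcome.

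Three things are unsettled. The ORR numerator demands something the visit schedule does not provide. The two endpoints treat patients without measurable disease differently. The CBR clock is not tied to a visit that falls at different times after randomisation in the two arms. Two programmers working from the same data could report different rates.

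**Working it through.** **Plan's own figures.** The documents state no design figure for ORR or CBR. The only ones are the power tables for the primary endpoint (70 per arm, one-sided 0.025). They reproduce (for example 69.6% against the stated 69%, and 82.2% against 82%) and are not in question here.

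**1. Confirmation.** Protocol Tables 18 and 19 derive response from a single assessment. The only nearby mention of confirming anything is the advice in Protocol 7.1.11 to biopsy or aspirate a doubtful residual lesion before calling a CR; it does not cover PR. A CR or PR first seen at the end visit has no later protocol scan. It can count as confirmed only if an earlier local scan is accepted as the second observation. So, on a two-scan reading:

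reported ORR = true ORR × share of responders with a confirming scan.

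True rates come from Protocol Table 1 (EGF100151): 23.7% by independent review, 31.8% by investigator. The documents give no figure for the share, so the whole range is shown.

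| Share with confirming scan (assumed) | True 23.7% | True 31.8% |
|---|---|---|
| 0 | 0 | 0 |
| 0.25 | 5.9% | 8.0% |
| 0.50 | 11.85% | 15.9% |
| 0.75 | 17.8% | 23.85% |
| 1 | 23.7% | 31.8% |

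SAP section 1 gives 62 enrolled, so about 31 per arm. Full confirmation then means 0.237 × 31 = 7.3 to 0.318 × 31 = 9.9 responders per arm, and half confirmation 3.7 to 4.9.

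**2. Measurable disease.** The inclusion criteria do not require measurable disease, and Protocol Table 19 allows a CR in patients with non-measurable disease only. Under the SAP, such a patient is an ORR responder and a CBR non-responder. Under the protocol, the same patient is a non-responder for both. SAP section 4 does not list the change.

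**3. CBR timing, if the clock starts at randomisation.** 24 weeks is 24 × 7 = 168 days. Assume randomisation falls on the day of first study treatment. The nominal end visit is then 168 days after randomisation in control and 168 + 7 = 175 with octreotide. Both arms qualify on schedule.

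No window is given for the end visit. Borrowing the ±4 days allowed for cycle starts, control visits fall at 164–172 days and octreotide visits at 171–179. If the nine days are equally likely, 4/9 of control visits fall short of 168. Under the SAP 2.1.3.5 duration rule (stop minus start plus 1) it is 3/9, and a visit one day early still passes. No octreotide visit falls short.

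- *The 24 weeks qualifies SD only.* The pool at risk is CBR minus ORR: 29 − 23.7 = 5.3 points (independent) or 37 − 31.8 = 5.2 (investigator). Control loses 3/9 × 5.2 = 1.7 to 4/9 × 5.3 = 2.4 points.
- *It qualifies CR and PR too.* Control loses 3/9 × 29 = 9.7 to 4/9 × 37 = 16.4 points.
- *Offset.* The octreotide arm is at risk a week longer before assessment. With exponential PFS and a median of 27.1 weeks (Protocol Table 1), 0.5^(24/27.1) = 54.1% and 0.5^(25/27.1) = 52.8% are progression-free, a ratio of 0.9747. CBR falls by 29 × 0.0253 = 0.7 to 37 × 0.0253 = 0.9 points.

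Net difference in favour of octreotide: −0.7 to −0.9 points if no visit is early; +0.8 to +1.6 on the SD-only reading (at most 0.016 × 31 = 0.5 of a patient); +8.9 to +15.5 on the widest reading.

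**The case against.** The strongest reply is that the documents already discount these results. SAP 2.6.1.5 calls them exploratory, unpowered and to be read with caution. Protocol sections 2 and 9.3.3.2 admit that disease assessment is less rigorous than in earlier studies and varies between sites. No test is planned, and the trial has stopped for futility. This limits the consequence, but a warning about precision does not define a numerator.

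A reader might infer that ORR must come out near zero. The documents do not support that. They state no two-scan rule, local assessments are recorded when done, and an earlier local scan could support an end-visit response. Zero is the extreme of the range.

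A reader might also infer that CBR is tilted towards octreotide. That needs the clock to start at randomisation, which is only inferred from the general rule in SAP 2.1.3.2. Endpoint text can override that rule, as SAP 2.6.1.3 does by timing diarrhoea onset from the first lapatinib plus capecitabine dose. SAP 2.6.1.5 itself speaks of response after 24 weeks of treatment. With the clock at first dose, the asymmetry disappears. The larger net figures also need early control visits and the 24 weeks applied to CR and PR.

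The non-measurable-disease conflict is real but narrow: under Protocol Table 19 such patients can reach ORR only through a CR.

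**Conclusion.** Two faults stand on the text alone. The *confirmed* qualifier cannot be met by a response first documented at the only mandated post-baseline assessment, and it conflicts with the SAP's own description of ORR as the response after 24 weeks of treatment. Read literally, ORR is biased downwards by an unknown amount that depends on local scanning. The SAP's non-measurable-disease rule also differs between ORR and CBR and departs from the protocol without being listed.

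A third point is an omission: the start of CBR's 24 weeks and the end-visit window are unstated, while the arms differ by about 7 days from randomisation to the end visit. No material bias towards octreotide is established.

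The sizes assume that the EGF100151 rates carry over (its CBR required stable disease for at least 6 months, and Protocol section 2 warns that the data may not be comparable), a ±4-day end-visit scatter with uniform days, exponential PFS, and about 31 patients per arm. The primary endpoint is untouched. The impact is small, but the wording should be corrected before these rates are reported.

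**What to change.** 1. Delete *confirmed* from the SAP definition. Define ORR as investigator-assessed CR or PR at the End of Study/Withdrawal RECIST assessment, and label it unconfirmed.
2. Apply the protocol's non-measurable-disease rule to both ORR and CBR.
3. Define CBR as CR, PR or SD at the nominal week-24 assessment, timed from the first dose of lapatinib plus capecitabine in both arms, with a stated visit window. Re-anchoring alone would leave early visits ambiguous in both arms. This also settles whether the 24 weeks qualifies SD only. A responder who withdraws before the window would then count for ORR but not for CBR, and the SAP should say so.
4. List the changes in SAP section 4, because the confirmation requirement is protocol text too.

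The cost is SAP wording and programming, with no new data. The downside is that ORR becomes an unconfirmed rate.
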